#### 3.2 Secondary Objectives

##### Principal secondary endpoint:

The principal secondary endpoint is “Time to end of ear pain”. This time will be calculated on the basis of the patient diary entries..

End of ear pain is defined as the first day (morning or evening) on which there is no use of analgesics, the diary pain score is zero and remains zero for all subsequent visits until the end of the study.

Throughout the study, patient or caregiver should record ear pain severity twice daily (morning and evening prior to dosing) in the diary using a proper pain scale according to patient's age until the end of study (see Appendix 3):

- Patients younger than 7 years old will use the FLACC scale (it will be assessed by parents or caregivers).
- Patients from 7 years old to younger than 13 years old will record the pain using the Wong Baker Faces Pain Scale.
- And patients 13 years old and older will record the pain using a VAS scale.

The time to end of pain is the interval (in days) between the first dose of study medication and the time when the ear pain in the evaluable ear ended (pain was absent and remains absent until the end of the study without using analgesic). This time will be calculated on the basis of the patient diary entries.

If ear pain in the evaluable ear continues at the end of the study, the time to end of pain variable will be recorded as the length of time between the time of the first dose of study medication and the last time point when a pain measurement was recorded.

Patients who take rescue medication, discontinue or are lost to follow up, and for whom the pain persists at the time of the last observation, will be censored at maximum length (Day 17) in those cases when the diary information is not available.

Other secondary endpoints:

- Sustained microbiological cure
- Clinical cure at Visit 3 and Visit 4
- Microbiological success at Visit 3 and Visit 4
- Therapeutic cure (clinical+microbiological cure) at Visit 4
- Changes in Brighton grading at Visit 3 and Visit 4
- Changes in otorrhea at Visit 3 and Visit 4
- Changes in edema at Visit 3 and Visit 4
- Changes in otalgia assessed by the investigator at Visit 3 and Visit 4
- Adverse events

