## 5. STUDY POPULATION

### 5.1 Inclusion Criteria

1. Male or female, at least 6 months of age;
2. Patients with diagnosis of uncomplicated acute diffuse otitis externa of less than 21 days (3 weeks) duration, with a total symptom score of at least 5 as defined under Efficacy Parameters, in at least 1 ear. The individual symptom scores, as defined in Sections 7.1.1.1, 7.1.1.3, and 7.1.1.4, must be:
  - Otalgia: at least 2 (moderate or severe);
  - Edema: at least 2 (moderate or severe);
  - Otorrhea: at least 1 (mild, moderate or severe), with sufficient quantity of otorrhea to allow culture.
3. Patients with Brighton grading of II or III in at least 1 ear, as defined in Appendix 2.
4. Patients with otorrhea of sufficient volume for sampling for microbiological culture (sample must be taken at baseline visit prior to the first study dose).
5. Willingness to refrain from swimming through end of the study.
6. For adult patients, ability to understand and provide written informed consent  
For pediatric patients, signed informed consent from patient's legally authorized representative; also, if the patient is capable of providing assent, signed assent from the patient as applicable according to local regulations.
7. Females who are not pregnant, not lactating and are not planning a pregnancy. All females of childbearing potential (those who are not premenstrual, not postmenopausal or not surgically sterile) will be able to participate only if they have a negative urine pregnancy test prior to randomization, and if they agree to use adequate birth control methods to prevent pregnancy throughout the study.  
Adequate birth control methods included topical, hormonal-oral, implantable or injectable contraceptives; mechanical-spermicide in conjunction with a barrier such as condom or diaphragm; intrauterine device (IUD); or surgical sterilization of partner (must be  $\geq$  6 months post vasectomy). For non-sexually active females, abstinence was regarded as an adequate method of birth control; however, if the patient became sexually active during the study, she must have agreed to use adequate birth control methods as defined above for the remainder of the study.

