##### 7.1.1.2 *Pain (Otalgia)*

Otalgia in both ears will be assessed at Visits 1, 3, and 4. The investigator will ask the patient (or caregiver if patient is too young) to assess his or her level of pain on the day of the visit. If the patient has taken analgesic medication, he or she will be asked to assess the level of pain before taking the analgesic. For consistency, the assessment of otalgia should always be performed before the ear is examined. Assessments will be on the scale described in Blanch 2000. Otalgia will be assessed as:

- Severe (3) if it interferes with activities of daily living;
- Moderate (2) if it causes discomfort but does not interfere with activities of daily living;
- Mild (1) if there is awareness of pain but not much discomfort
- Absent (0) if there is total absence of pain.

At Visits 3 and 4, pain will be considered resolved if the pain level is 0. Otalgia will be considered improved if the pain level is lower than in the previous visit.

Moreover, patients will complete a diary twice daily in which they will record assessments of ear pain, pain medication use.

Throughout the study, patient or caregiver should record pain severity at least twice daily (prior to dosing). For patients under 7 years old, caregiver will complete the FLACC scale. Patients from 7 years old to younger than 13 years old will record the pain using the Wong Baker Faces Pain Scale. And patients 13 years old and older will record the pain using a VAS scale (see Appendix 3).

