##### ***10.1.10.2 Secondary efficacy endpoints***

Only analysis of the principal secondary endpoint will be confirmatory. Analysis of the other secondary efficacy endpoints will be supportive only. Since each confirmatory comparison (Ciprofloxacin 0.3% plus Fluocinolone acetonide 0.025% otic solution over Ciprofloxacin 0.3% otic solution alone and over Fluocinolone acetonide 0.025% otic solution alone for the primary endpoint, and for the principal secondary endpoint) should be

statistically significant at a two-sided 0.05 significance level, no adjustment for multiple comparisons/multiplicity will be made.

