### **Principal secondary endpoint**

#### Time to end of ear pain

Patients or caregivers will complete a diary twice daily (prior to dosing) in which they will record assessments of ear pain and pain medication use, including the time and date of the assessment.

Ear pain is defined as ending on the first day (morning or evening) on which there is no use of analgesics, the diary pain score is zero and the score remains at zero for all subsequent visits until the end of the study.

The patient diary information together with investigator assessment will be used to ascertain the time point (morning or evening) and date at which the ear pain in the evaluable ended without use of analgesics. The time to end of ear pain is the interval (in days) between the first dose of study medication and the time when the ear pain in the evaluable ended without use of analgesics.

If ear pain in the evaluable ear continued to the end of the study, the TEOP will be recorded as the length of time between the time of the first dose of study medication and the last time point when a pain measurement was recorded.

Patients who took rescue medication, discontinued or were lost to follow up, and for whom the pain persisted at the time of the last observation, will be censored at maximum length (Day 17) in those cases when the diary information is not available.

The null hypothesis is that there is no difference in time to end of pain between the combination and the components alone. The alternative hypothesis is that there is a difference in time to end of pain between the combination and the components alone. The comparison of the treatment groups will be made by using the log-rank test stratified on age (6 months to younger than 18 years old versus 18 years and older), and a difference will be claimed if the null hypothesis can be rejected at the two-sided 0.05 level.

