- In patients with treatment failure (including rescue medication with otic or systemic antibiotics), the TEOP will be censored at the maximum value (17 days).
- Patients who discontinue or are lost to follow up, and for whom the pain persisted at the time of the last observation, will be censored at maximum length (17 days) in those cases when the diary information is not available.

The null hypothesis is that there is no difference in time to end of pain between the combination and the components alone. The alternative hypothesis is that there is difference in time to end of pain between the combination and the components alone. The comparison will be made using the log-rank test stratified on age (6 months to <18 years versus ≥ 18 years). The p-value will be shown for each comparison between the combination and individual component. The median TEOP will be calculated using the Kaplan Meier method and will be presented with its 95% CI for each treatment group.

Kaplan Meier plots will also be shown by treatment group and strata.

Sensitivity analysis of “time to end of pain” will be performed by using the full information as assessed from patient diaries without regard for the patient’s need for analgesic therapy.

Sustained Microbiological Outcome

For any patient with a culture positive for a pathogen at Visit 1, bacteriological response at Visits 3 will be classified as Eradication, Presumed Eradication, Persistence, Presumed Persistence, Superinfection or Indeterminate and bacteriological response at Visit 4 will be classified as Eradication, Presumed Eradication, Persistence, Presumed Persistence, Recurrence, Superinfection, Reinfection or Indeterminate, as defined in Section 4.7.2.

The number and percentage of patients with each response will be summarized by visit and treatment group. The proportion of patients with sustained microbiological cure i.e. with a response of Eradication or Presumed Eradication at both Visit 3 and Visit 4 will be compared between the treatment groups by using the same chi-squared test as the primary efficacy endpoint.

If a patient took rescue medication prior to Visit 4, he/she will be considered to not have achieved sustained microbiological cure.

A by-patient listing of sustained microbiological outcome will be provided.

Overall Clinical Outcome

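### The confirmatory log-rank test of time to end of ear pain is valid but leaves out Visit 1 otalgia; adding it as a stratum costs almost nothing and may recover power if starting pain is prognostic

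*SAP*

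**What the plan says.** **The test.** SAP 4.7.3 (Time to End of Ear Pain) states: "The comparison will be made using the log-rank test stratified on age", with two strata, under 18 years and 18 years or older. SAP 4.7.1 gives the same test at a 5% level. Protocol 10.1.10.2 agrees: "The comparison of the treatment groups will be made by using the log-rank test stratified on age", and "a difference will be claimed if the null hypothesis can be rejected at the two-sided 0.05 level". The combination is compared with each component separately.

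**Its status.** Protocol 10.1.10.2: "Only analysis of the principal secondary endpoint will be confirmatory" among the secondary endpoints.

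**The event.** Pain ends at the first diary time point with a zero score and no analgesic, provided the score stays at zero to the end of the study. SAP 4.7.3 censors treatment failures at 17 days.

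**Starting pain.** Protocol 7.1.1.2: "Otalgia in both ears will be assessed at Visits 1, 3, and 4". One 0-3 scale serves all ages. Protocol 5.1 requires a score of at least 2, so eligible patients are either moderate (2) or severe (3).

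**Where starting pain is used.** SAP 4.7.3 tabulates otalgia by visit, but no TEOP analysis uses the Visit 1 grade. The subgroup Cox models in SAP 4.7.1.4 contain treatment, age group and ear wick placement. The TEOP sensitivity analysis in SAP 4.7.3 changes only the analgesic rule.

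**Why age is a stratum.** Protocol 5.5 explains that enrolment is stratified to represent both age groups, not for a statistical reason.

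**The synopsis differs.** Its Statistical Methods paragraph attaches the age-stratified log-rank test to therapeutic cure and gives TEOP a log-rank test with no strata.

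**The concern.** Time to zero pain plausibly depends on how much pain there was at the start. When a prognostic factor is left out of a log-rank test, patients who recover quickly leave the risk set first, and they leave sooner in the better arm. The later risk sets in that arm are then richer in slow recoverers, and the treatment difference is pulled toward the null. Stratifying on the factor avoids this.

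The stake is the TEOP claim. Both comparisons must reach two-sided 0.05, one of them against the smaller fluocinolone arm, and the trial was sized for therapeutic cure rather than for TEOP. The factor is already collected, so any power recovered would be nearly free.

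**Working it through.** **1. The plan's own figure.** SAP 4.10 sizes the primary endpoint only: 62% against a relative increase of 25% (62% x 1.25 = 77.5%, stated as 78%), two-sided 5%, 80% power, 150 per group. The two-proportion formula with 62% and 77.5% gives 137 per group without continuity correction and 150 with it. The total of 500 also reproduces: 375 / (1 - 0.25) = 500. Neither figure concerns TEOP, for which the documents state no hazard ratio, event count or power.

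**2. What TEOP can detect.** Schoenfeld: HR = exp[(1.96 + 0.842) / sqrt(D x a x (1 - a))], where D is events and a is the share in the combination arm. The event counts are assumptions: 80% or 100% of the 300 or 225 patients.

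| Comparison | Events | HR for 80% power |
|---|---|---|
| vs ciprofloxacin, 150:150 | 300 | 1.38 |
| vs ciprofloxacin, 150:150 | 240 | 1.44 |
| vs fluocinolone, 150:75 | 225 | 1.49 |
| vs fluocinolone, 150:75 | 180 | 1.56 |

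The default efficacy population, MITT-PA/SA (SAP 4.4), is a subset of the pathogen-positive patients that the 375 counts, so these numbers may be optimistic.

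**3. Age strata against age x otalgia strata.** The statistic, summed over strata and event times, is Z = sum(d1 - d x n1/n) / sqrt(sum[d x (n1/n) x (1 - n1/n) x (n - d)/(n - 1)]), rejecting at |Z| > 1.96.

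From the documents: arm sizes, twice-daily diary, Day 17 limit. Assumed: exponential times, control median 5 days, half the patients severe, half in each age group, age hazard ratio 1.2. Prognostic HR means the hazard of pain ending in moderate relative to severe patients. The treatment HR in each column was set to give about 76-79% power when otalgia has no effect. There were 3,000 replicates per cell, with Monte Carlo error of about 0.8 point per power figure.

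Power in %, age only -> age x otalgia:

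| Prognostic HR | 150:150, HR 1.40, no failures | 150:75, HR 1.51, no failures | 150:150, HR 1.60, 10% failures | 150:75, HR 1.80, 10% failures |
|---|---|---|---|---|
| 1.0 | 77.9 -> 77.5 | 79.1 -> 78.0 | 77.0 -> 77.1 | 76.1 -> 75.5 |
| 1.25 | 79.2 -> 79.0 | 77.5 -> 76.8 | 75.9 -> 76.4 | 74.5 -> 74.9 |
| 1.5 | 76.4 -> 78.4 | 77.0 -> 78.4 | 76.2 -> 77.6 | 74.4 -> 75.3 |
| 2.0 | 71.7 -> 78.9 | 71.7 -> 77.7 | 71.6 -> 75.4 | 71.0 -> 74.8 |
| 3.0 | 62.0 -> 76.1 | 61.4 -> 75.5 | 65.5 -> 73.2 | 64.9 -> 73.5 |

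In the last two columns, 10% of patients are treatment failures censored at Day 17 whatever their starting pain. These columns give the lower ends of the range.

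**4. Type I error.** With no treatment effect and a prognostic HR of 2.0 (4,000 replicates), rejection was 4.4% with age strata and 4.5% with age x otalgia strata.

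**5. Second simulation.** A separate run (150:150, treatment HR 1.4, median about 4 days, age HR 0.8, no failures) let severe pain multiply the hazard by 0.6, 0.5 or 0.4, which are prognostic HRs of 1.67, 2.0 and 2.5. Power went from 75.8 to 78.9, 73.1 to 78.7 and 68.6 to 79.8, in line with the no-failure columns.

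**The case against.** **The planned test is not wrong.** It is pre-specified, uses the enrolment stratum and holds its error rate. A reader might infer that it is biased because randomisation does not balance on otalgia. It is not: chance imbalance is already covered by the 5% level. This objection stands, and the point is one of efficiency only.

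**The loss is not established.** A reader might infer that power is certainly being thrown away. The documents do not support that. They give no prognostic strength and no moderate/severe split, and eligibility leaves only two otalgia levels, which limits what the factor can explain. With 80% severe, the second simulation showed a gain of about 0 at a multiplier of 0.7, 2 points at 0.6 and 3 at 0.4. This also stands.

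**Day 17 censoring shrinks the gain.** The 10% columns raise the treatment HR to keep power near 77%. With 10% failures and treatment HRs of 1.41 and 1.53, power without an otalgia effect is only about 52%, and the gain is about 2-4 points at a prognostic HR of 2.0 and 6-7 at 3.0 (severe share 50% or 30%). With 15% failures and HR 1.4, power is about 37%, and the gains are 1.2, 2.3 and 4.0 points at multipliers of 0.6, 0.5 and 0.4. If the trial is weakly powered for TEOP, this change does not rescue it.

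**Two further inferences fail.** A reader might add that pooling three diary pain scales under age 18 weakens the test. The event is zero on whichever scale applies, and SAP 4.7.1.4 already models TEOP by 6 months to <7, 7 to <13 and 13 years or older, the same cut-points as the scales. A reader might also cite the sponsor's earlier 590-patient trial, which found no significant difference in mean TEOP (protocol 2.1). That was a non-inferiority trial of a different regimen in patients aged 7 and older, and it says nothing about whether baseline pain predicts TEOP.

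What survives is the asymmetry. The largest cost seen when otalgia had no effect was 1.1 points, against a possible gain several times larger.

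**Conclusion.** The concern holds as a conditional, low-cost improvement, not as an error. The confirmatory TEOP test is valid but leaves a plausible predictor, known for every patient, out of the analysis. If baseline otalgia is prognostic, adding it gains about 0 points of power at a prognostic HR up to 1.25, 1-2 at 1.5, 4-7 at 2.0 and 8-14 at 3.0. The lower ends apply with about 10% of patients censored at Day 17 as failures.

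The range assumes about half the patients severe, 150:150 or 150:75, and a treatment effect large enough for roughly 76-79% power. It is smaller if the true effect is weaker, failures are more common or the severity split is very uneven. It becomes material only from a prognostic HR of about 2, and the documents cannot show whether that is reached.

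**What to change.** Before unblinding and database lock:

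- In protocol 10.1.10.2 and SAP 4.7.1 and 4.7.3, stratify the TEOP log-rank test on age group (<18, 18 or older) x Visit 1 otalgia of the evaluable ear (2 or less, 3), giving four strata. The lower category also places any randomised patient who did not meet the entry score.
- In the synopsis (Statistical Methods), give TEOP the same stratified test, and reconcile the paragraph that attaches a log-rank test to therapeutic cure with the chi-squared test in protocol 10.1.10.1.
- State in SAP 4.7.3 whether the Kaplan-Meier plots by strata use age alone or all four strata.

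No extra analysis by pain scale is needed, given SAP 4.7.1.4.

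The cost is a sentence in each place and one more stratification variable, with no new data and no change to randomisation. The downside is smaller strata: in the fluocinolone comparison, (150 + 75) / 4 = about 56 patients each if evenly split. SAP 4.11 allows revisions finalised before database lock. Made after unblinding, the change would be post hoc and could not support the confirmatory claim.

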#### 7.1.1.3 *Edema*

Edema in both ears will be assessed at Visits 1, 3, and 4 by the investigator. For consistency, the same individual should perform the assessments at all 3 visits, if possible. Edema will be assessed as:

- Severe (3) if the tympanic membrane is not visible because of swelling;
- Moderate (2) if the tympanic membrane is partially visible;
- Mild (1) if there is some swelling but the tympanic membrane is fully visible;
- Absent (0) if there is no visible swelling.

At Visits 3 and 4, edema will be considered resolved if the edema level is 0. Edema will be considered improved if the edema level is lower than in the previous visit.

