#### 7.1.1.5 *Overall Clinical Outcome*

Overall Clinical Outcome is based on the Total signs/symptoms score (TSSS), which is calculated by the sum of otalgia score + edema score + otorrhea score. Patients will be allocated to one of the following categories for Overall Clinical Outcome:

1. Clinical Cure: TSSS is 0, as defined in Sections 7.1.1.2, 7.1.1.3 and 7.1.1.4.
2. Clinical Improvement: TSSS is different than 0 but lower than the previous visit, as defined in Sections 7.1.1.2, 7.1.1.3 and 7.1.1.4.
3. Clinical Failure: TSSS does not meet the definitions of Clinical Cure or Clinical Improvement, as defined in Sections 7.1.1.2, 7.1.1.3 and 7.1.1.4.
4. Indeterminate: Discontinued (for reasons other than Clinical Failure) or lost to follow-up.

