- Persistence if any pathogen cultured at Visit 1 is still present;
- Presumed Persistence if the Overall Clinical Outcome is Clinical Failure but no culture result is available from Visit 3;
- Superinfection if a pathogen not present at Visit 1 is now present (presence of a nonpathogenic organism will not be considered Superinfection); or
- Indeterminate if none of the above definitions are met and the bacteriologic response cannot be determined.

For any patient with a culture positive for a pathogen at Visit 1, bacteriologic response at Visits 4 will be classified as:

- Eradication if the culture does not show growth of any pathogen;
- Presumed Eradication if there is no material to culture and the Overall Clinical Outcome is Clinical Improvement or Clinical Cure as above;
- Persistence if any pathogen cultured at Visit 1 is still present;
- Presumed Persistence if the Overall Clinical Outcome is Clinical Failure but no culture result is available from Visit 4;

- Recurrence if there is reappearance of the pathogen eradicated or presumably eradicated at Visit 3;
- Superinfection if a pathogen not present at Visit 1 and Visit 3 is now present (presence of a nonpathogenic organism will not be considered Superinfection);
- Reinfestation if there is isolation of a new pathogen different from the one eradicated or presumably eradicated at Visit 3; or
- Indeterminate if none of the above definitions are met and the bacteriologic response cannot be determined.

For any patient with a negative culture or a culture positive for a non-pathogen at Visit 1, bacteriologic response at Visits 3 will be classified as:

- Presumed Eradication if the culture does not show growth of any pathogen or if there is no material to culture and the Overall Clinical Outcome is Clinical Improvement or Clinical Cure as defined above;
- Presumed Persistence if the Overall Clinical Outcome is Clinical Failure but no culture result is available from Visit 3;
- Superinfection if a pathogen not present at Visit 1 is now present; or
- Indeterminate if none of the above definitions are met and the bacteriologic response cannot be determined.

For any patient with a negative culture or a culture positive for a non-pathogen at Visit 1, bacteriologic response at Visits 4 will be classified as:

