Overall Clinical Outcome is based on the TSSS, which is calculated by the sum of otalgia score + edema score + otorrhea score. Patients will be allocated to one of the following categories for Overall Clinical Outcome:

1. Clinical Cure: TSSS is 0
2. Clinical Improvement: TSSS is different than 0 but lower than the previous visit
3. Clinical Failure: TSSS does not meet the definitions of Clinical Cure or Clinical Improvement.
4. Indeterminate: Discontinued (for reasons other than Clinical Failure) or lost to follow-up

Overall clinical outcome will be summarized by treatment group and visit in terms of proportion in each category at each visit.

Responses will be categorized into two groups for analysis. Clinical improvement, Clinical Failure, and indeterminate will be collapsed into a single category: Clinical Failure. Overall clinical outcome will be analyzed using the same method as the primary efficacy endpoint. A Pearson’s Chi Squared test for independence will be used to test that there is no difference between the combined treatment and each individual component at Visits 3 and 4.

If a patient took rescue medication prior to Visit 3, the response will be considered a clinical failure at Visit 3. Similarly, if a patient took rescue medication prior to Visit 4, the response will be considered a clinical failure at Visit 4.

A by-patient listing of overall clinical outcome will be provided.

Microbiological Outcome

Microbiological Outcome is described in Section 4.7.2.

Microbiological outcome will be summarized by treatment group and visit in terms of proportion in each category at each visit.

If a patient took rescue medication prior to Visit 3, the response will be considered a failure at Visit 3. Similarly, if a patient took rescue medication prior to Visit 4, the response will be considered a failure at Visit 4.

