If a patient took rescue medication prior to Visit 3, the response will be considered not resolved at Visit 3. Similarly, if a patient took rescue medication prior to Visit 4, the response will be considered not resolved at Visit 4.

For Visits 3 and 4, the proportion of patients with a response of Resolved and Not Resolved will be compared between the treatment groups by using the same Chi-squared test as the primary efficacy endpoint.

A by-patient listing of edema data will be provided.

Otorrhea

Otorrhea will be assessed by the Investigator at Visits 1, 3 and 4. Otorrhea will be assessed as Severe, Moderate, Mild, or Absent as defined in Section 4.7.2.

The number and percentage of patients with each outcome (Severe, Moderate, Mild or Absent) will be summarized by visit and treatment group.

Assessments will also be summarized in terms of a 3-level and a 2-level response. For the 3-level response, otorrhea will be considered resolved at Visits 3 and 4 if the otorrhea is assessed as Absent. Otorrhea will be considered as "Improved" at Visit 3 and Visit 4 if otorrhea is assessed by the investigator as "Mild" and was assessed as "Severe" or "Moderate" at Visit 1 (Day 1) or if otorrhea was assessed by the investigator as "Moderate" at Visit 3 or Visit 4 and was assessed as "Severe" at Visit 1. Otorrhea will be considered as "Not Improved" otherwise. Furthermore if otorrhea is considered "Not Improved" or "Improved" in the 3-level response then it will be identified as "Not Resolved" in the 2-level response. If otorrhea is considered "Resolved" in the 3-level response then it will also be considered "Resolved" in the 2-level response.

If a patient took rescue medication prior to Visit 3, the response will be considered not resolved at Visit 3. Similarly, if a patient took rescue medication prior to Visit 4, the response will be considered not resolved at Visit 4.

For Visits 3 and 4, the proportion of patients with a response of Resolved and Not Resolved will be compared between the treatment groups by using the same Chi-squared test as the primary efficacy endpoint.

A by-patient listing of otorrhea data will be provided.

Ear Pain Scales

Ear pain scales will be assessed by the patient twice a day in the patient's Diary Card to calculate the TEOP. The ear pain scales assessed at Visit 3 and Visit 4 will be categorized as follows:

- Disappeared if there is no ear pain
- Improved if the response is better than the response at Visit 1

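### Judging Clinical Improvement at Visit 4 against Visit 3 misclassifies some dry-eared patients in two supportive microbiological endpoints

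*SAP*

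**What the plan says.** Overall Clinical Outcome rests on the total signs/symptoms score (TSSS), the sum of otalgia, edema and otorrhea, each scored 0 to 3. A TSSS of 0 is Clinical Cure. The next category in SAP 4.7.3 is "Clinical Improvement: TSSS is different than 0 but lower than the previous visit"; protocol 7.1.1.5 likewise has "TSSS is different than 0 but lower than the previous visit". Any other scored result is a failure: "Clinical Failure: TSSS does not meet the definitions of Clinical Cure or Clinical Improvement".

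The category then decides the bacteriologic response when there is no culture. In SAP 4.7.2 (and protocol 7.1.2), a patient with a baseline pathogen is "Presumed Persistence if the Overall Clinical Outcome is Clinical Failure but no culture result is available from Visit 4". With no material to culture and Clinical Improvement or Cure, the response is Presumed Eradication. The schedule of observations says that a dry ear is not cultured.

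SAP 4.7.3 counts Eradication and Presumed Eradication as favorable and Presumed Persistence as unfavorable. Sustained microbiological cure needs a favorable response at both Visit 3 and Visit 4.

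The reference visit is not uniform:

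- **Previous visit:** TSSS; the improved definitions for otalgia, edema and otorrhea in protocol 7.1.1.2 to 7.1.1.4; and Brighton grading in protocol 10.1.10.2 and SAP 4.7.3.
- **Visit 1:** the 3-level otalgia, edema and otorrhea responses in SAP 4.7.3, and its ear pain scales ("Improved if the response is better than the response at Visit 1").

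**The concern.** At Visit 3 the previous scored visit is baseline, so the rule asks whether the patient is better than at entry. At Visit 4 it asks whether the patient has improved further since the end of treatment. A patient who improved greatly by Visit 3 and then held steady at a small residual score has not, and is labelled a failure. A patient still near the baseline score needs only a one-point drop to be labelled improved.

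In a dry ear that label alone determines the microbiological result. An unchanged ear can thus move from presumed eradicated to presumed persistent between visits without any culture evidence. Two named secondary endpoints with formal between-group tests use that result.

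**Working it through.** No figure in the plan bears on this point, and the sample size calculation does not enter. The check applies the stated rules to possible score paths.

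**Inputs**

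- Scored visits: protocol 7.1.1.3 states "Edema in both ears will be assessed at Visits 1, 3, and 4 by the investigator", and 7.1.1.2 and 7.1.1.4 give the same visits for otalgia and otorrhea. Visit 2 is a telephone call. I take the previous visit to mean the previous scheduled scored visit.
- Entry: protocol 5.1 requires otalgia at least 2, edema at least 2 and otorrhea at least 1, "with a total symptom score of at least 5 as defined under Efficacy Parameters". Baseline TSSS therefore runs from 2 + 2 + 1 = 5 to 3 + 3 + 3 = 9.
- Dry ear: otorrhea is 0, so the largest possible TSSS is 3 + 3 + 0 = 6.
- Conditions: baseline pathogen present, no rescue medication, and no discharge (hence no culture) at Visit 4. For sustained cure in the first three paths below, the ear is also dry at Visit 3.

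**Rules compared at Visit 4, for TSSS above 0**

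- As written: Improvement if V4 < V3, otherwise Failure.
- Proposed: Improvement if V4 < V1 and V4 ≤ V3, otherwise Failure.
- Without a culture, Improvement gives Presumed Eradication (favorable) and Failure gives Presumed Persistence (unfavorable).

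| V1-V3-V4 | As written | Proposed |
|---|---|---|
| 7-1-1 | 1 < 1 is false: unfavorable | 1 < 7 and 1 ≤ 1: favorable |
| 7-4-4 | 4 < 4 is false: unfavorable | 4 < 7 and 4 ≤ 4: favorable |
| 7-6-5 | 5 < 6: favorable | 5 < 7 and 5 ≤ 6: favorable |
| 5-7-6 | 6 < 7: favorable | 6 < 5 is false: unfavorable |
| 7-0-1 | 1 < 0 is false: unfavorable | 1 ≤ 0 is false: unfavorable |
| 7-1-2 | 2 < 1 is false: unfavorable | 2 ≤ 1 is false: unfavorable |

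**Sustained microbiological cure as written**

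- 7-1-1: Visit 3 is Improvement (1 < 7), so Presumed Eradication; Visit 4 is Presumed Persistence. Not achieved.
- 7-4-4: the same sequence. Not achieved.
- 7-6-5: Visit 3 can be otalgia 3, edema 3, otorrhea 0, and 6 < 7, so Presumed Eradication; Visit 4 is also Presumed Eradication. Achieved.
- 5-7-6: a Visit 3 score of 7 exceeds the dry-ear maximum of 6, so discharge is present and the Visit 3 culture decides that visit. The anomaly is in the Visit 4 outcome: a score one point above entry counts as presumed eradicated.

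**What does not move**

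At Visit 3, V3 < V1 is the test under both rules. Therapeutic cure needs TSSS 0 at either visit, and the clinical cure tests in SAP 4.7.3 pool Improvement with Failure.

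**The case against.** The rule is explicit and has a coherent reading: residual signs that stop improving are conservatively presumed to reflect persisting infection. The SAP's per-pathogen definition uses a similar idea, persistent or worsening signs, though it names no reference visit. Conservatism does not explain why 5-7-6 is presumed eradicated, or why a dry ear at TSSS 1 is worse than one at 5. This part of the objection therefore fails.

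Three parts stand.

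- A reader might infer that the rule penalises the faster-acting arm, whose patients have less room to fall after Visit 3. The documents do not support that. Patients who reach TSSS 0 and remain there cannot be affected, and slow plateaus such as 7-4-4 are hit as well. The net direction depends on score trajectories that the documents do not give. The Visit 4 microbiological test also compares each ciprofloxacin-containing arm with fluocinolone, not the combination with ciprofloxacin.
- A reader might infer that the TSSS rule stands alone against every related definition. It agrees with protocol 7.1.1.2 to 7.1.1.4 and with Brighton grading; the mismatch is with the 3-level responses and the ear pain scales.
- The endpoints carry little weight: protocol 10.1.10.2 makes all secondary endpoints other than the principal one supportive only.

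The high-score examples are also uncommon in kind. A dry-ear TSSS of 6 means severe pain and severe edema with no rescue medication.

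**Conclusion.** The point holds as a misclassification in two supportive secondary endpoints, Visit 4 microbiological outcome and sustained microbiological cure. It applies to patients without rescue medication or a Visit 4 culture. The plainest case is an unchanged, non-zero TSSS below baseline, which is scored unfavorable; 5-7-6 shows an error in the opposite direction. The number of patients affected and the sign of any between-arm bias cannot be derived from the documents, so I claim neither.

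The primary analysis, the Visit 4 therapeutic cure test and the clinical cure tests are unaffected. I make no claim about time to end of ear pain: its censoring rule in SAP 4.7.3 mentions treatment failure without tying it to this category. The change is worth making because it is cheap and the rule gives results that are hard to defend, but no confirmatory conclusion is shown to depend on it.

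**What to change.** Before database lock, define Clinical Improvement in protocol 7.1.1.5 and SAP 4.7.3 as TSSS above 0, lower than at Visit 1 and not higher than at the previous visit. State that the analysis category is derived from the recorded scores, because protocol 8.2.3 and 8.2.4 also have the investigator evaluate Overall Clinical Outcome. Align the improved definitions in protocol 7.1.1.2 to 7.1.1.4, and the Brighton Improved category in both documents, to the same reference. Correct the pointer in SAP 4.7.2, which cites a definition of Clinical Improvement above although it appears only in 4.7.3.

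The cost is a few sentences in each document and some programming. No new data are needed, and SAP 4.11 allows planned analyses to be revised before lock.

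The change does not remove every odd ordering: 7-1-2 stays unfavorable beside a favorable 7-6-5. That is the price of keeping a relapse such as 7-0-1 as a failure, which a plain Visit 1 reference would not do.
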